12.2 Collection, Recording and Reporting of Adverse Events

All events meeting the definition of an AE must be collected and reported from screening (visit 1) until End of Trial and at potential Follow-Up visits. During each contact with the trial site (visit or telephone, excluding safety visits, where the patient is not seeing the Investigator or site staff e.g. visits to the laboratory) the patient must be asked about adverse events, e.g. "Have you experienced any problems since the last contact?"

All AEs, either observed by the Investigator or reported by the patient, must be recorded by the Investigator and evaluated. Novo Nordisk' assessment of expectedness is done according to the reference documents: N8 Investigator's Brochure (insert reference)

The Investigator should record the diagnosis, if available. If no diagnosis is available then the Investigator should record each sign and symptom as individual AEs.

All AEs must be recorded by the Investigator on the standard AE form. If more than one sign or symptom is to be reported use a separate AE form for each sign and symptom. For SAEs complete a safety information form for each event. However, if several symptoms or diagnosis occur as part of the same clinical picture only one set of safety information form pages can be used to describe all the SAEs.

MESIs and other events for expedited reporting must always be reported to Novo Nordisk on the AE form and the safety information form, irrespective of seriousness within the same timelines as for SAEs.

The Investigator must report initial information on all SAEs, MESIs and other events for expedited reporting to Novo Nordisk within **24 hours** of obtaining knowledge about the event.

The Investigator must complete and forward electronically in pdf format/fax copies to Novo Nordisk:

- AE form in the eCRF **within 24 hours**
- safety information form on the paper CRFs **within 5 calendar days**

of obtaining knowledge about the SAE.

If for some reason the EDC application is unavailable then the AE information should be reported to Novo Nordisk by fax, telephone or e-mail within the same timelines.

For US the Investigator, and for all other countries Novo Nordisk, must inform the regulatory authorities and IECs/IRBs in accordance with the local requirements in force and ICH GCP⁸.

Novo Nordisk will notify the Investigator of trial product related suspected unexpected serious adverse reactions (SUSARs) in accordance with the local requirements. In addition, the Investigator will be informed of any trial related procedure SAEs that may warrant a change of any trial procedure.

Investigators will be notified of trial-related SAEs in accordance with the local requirements in force and ICH GCP⁸. In Japan, Novo Nordisk must inform the health authorities and the relevant parties of SAE information in accordance with the Japanese requirements in force and ICH GCP.⁸

The monitor must be informed accordingly.

12.2.1 Disease-related Bleeding

Bleeds and other symptoms (e.g. pain, swelling, synovitis, arthralgia, injection site haematoma) in connection to bleeds that are evaluated by the Investigator as part of the underlying disease are AEs. However, they should only be reported as AEs if evaluated as related to trial product or trial procedure by the Investigator. Furthermore, fatal or life-threatening SAEs must be reported regardless of relatedness. All bleeds and other symptoms related to the underlying disease will be captured in the eCRF.

12.2.2 Follow-up of Adverse Events

During and following a patient's participation in a clinical trial, the Investigator should ensure that adequate medical care is provided to the patient for any AE, including clinically significant laboratory values related to the trial. The Investigator should inform the patient when medical care is needed for AE(s) of which the Investigator becomes aware.

The follow up information should only include new (updated and/or additional) information that reflects the situation at the time of the Investigator's signature.

Follow-up information (corrections, new or additional information) should be reported **within 24 hours** of obtaining knowledge of the information for SAEs, and if previously non-serious AEs become SAEs.

All non-serious AEs classified as severe or possibly/probably related to the trial product must be followed until the patient has "recovered" or "recovered with sequelae", and all queries have been resolved. Cases of chronic conditions or cancer or AEs ongoing at time of death (i.e. patient dies from another AE) can be closed with an outcome of "recovering" or "not recovered". Cases can be closed with an outcome of "recovering" when the patient has completed the post-trial follow-up period and is expected by the Investigator to recover.

All other non-serious AEs must be followed until the outcome of the event is "recovering", "recovered" or "recovered with sequelae" or until the end of the post-treatment follow-up stated in the protocol, whichever comes first, and until all queries related to these AEs have been resolved. AEs ongoing at time of death (i.e. patient dies from another AE) can be closed with an outcome of "recovering" or "not recovered".

The Investigator must ensure that the worst case severity and seriousness is kept consistent.

The Investigator must record follow-up information on non-serious AEs by updating the AE form in the eCRF. The follow-up information should only include new (updated and/or additional) information that reflects the situation at the time of the Investigator's signature.

Queries or follow-up requests from Novo Nordisk should be responded to within 14 calendar days, unless otherwise specified. The Investigator must forward follow-up information on SAEs, MESIs and other events for expedited reporting within 5 calendar days of obtaining the information. This must be done by updating the AE form in the eCRF and/or completing a new safety information form marked follow-up on paper CRF and forwarding these to Novo Nordisk. If for any reason the EDC application is unavailable, then fax, telephone or e-mail to Novo Nordisk.

All SAEs, MESIs and other events for expedited reporting must be followed up until the outcome of the event is “recovered”, “recovered with sequelae” or “fatal” and until all queries have been resolved. Cases of chronic conditions or cancer or AEs ongoing at time of death (i.e. the patient dies from another AE) can be closed with the outcome of “recovered” or “not recovered”. Cases can be closed with an outcome of “recovering” when the patient has completed the trial and is expected by the Investigator to recover.

After access to update the AE form in EDC is removed the Investigator must record any follow-up information, if required, of SAE, MESI and other events for expedited reporting on the paper CRFs provided at trial closure.

12.3 Technical Complaints and Technical Complaint Samples

12.3.1 Collection and Reporting of Technical Complaints

All technical complaints, as defined in Section [12.1](#) - occurring from the time of first and until the last usage of trial supplies - must be collected and reported to Novo Nordisk.

The patient must be asked about technical complaints during each contact (visit or telephone) with the Investigator or trial site staff. This may be done by posing a simple question such as “have you experienced any problems since the last contact?”.

The Investigator must assess whether the technical complaint is related to:

- AE(s), SAE(s), MESI(s) and/or other events for expedited reporting

The AE(s), SAE(s), MESI(s) and/or other events for expedited reporting related to technical complaint(s) must be reported by the Investigator following the same reporting requirements and timelines as for other AEs, SAEs, MESIs and other events for expedited reporting (see section [12.2](#)).

Technical complaints must be reported on the technical complaint form by the Investigator, as described in the following:

One technical complaint form must be completed for each trial product, non-investigational medicinal product or auxiliary supply. If the technical complaint involves more than one batch number, a technical complaint form for each batch number must be completed.

The Investigator must fax the technical complaint form to *Customer Complaint Center, Novo Nordisk, [contact]*, within the following timelines of the trial site obtaining knowledge of the technical complaint:

- technical complaint assessed as related to a **SAE and/or MESI within 24 hours**
- all other technical complaints within **5 calendar days**

12.3.2 Collection, Storage and Shipment of Technical Complaint Samples

The Investigator must collect the technical complaint sample from the patient. If the technical complaint sample is unobtainable, the Investigator must specify on the technical complaint form why it is unobtainable.

The **technical complaint sample** and a **paper copy of the technical complaint form** must be sent to Novo Nordisk within **5 calendar days** of receiving the technical complaint sample at trial site by using the following address:

Novo Nordisk A/S, Att.: Customer Complaint Center, [name]

The Investigator must ensure that the technical complaint sample is labelled with the batch number and, if available, the DUN number.

Storage and shipment of the technical complaint sample should be done in accordance with the conditions prescribed for the product, see Section 9. For further details on the shipment conditions of technical complaints, please contact the local monitor.

12.4 Precautions/Over-Dosage

As with any protein injected i.v., hypersensitivity reactions may occur. This might include rash, pruritus, fever, nausea, headache, and vomiting; also changes in blood pressure may occur.

If any of the above events occur or if an overdose is suspected, further N8 administration should be stopped and the patient should receive treatment as appropriate according to the hospital practice and guidelines.

12.5 Safety Committee(s)

12.5.1 Internal Novo Nordisk Safety Committee

Novo Nordisk will constitute an internal safety committee to perform ongoing safety surveillance of N8. The safety committee works according to a written guideline and will meet regularly to discuss and evaluate the overall safety for N8 for this trial and all other N8 trials. The Novo Nordisk safety committee can take action with regard to the patient safety for the trial based upon observations of the overall information for N8. Pre-defined rules for setting the enrolment on hold is described in Section [12.5.2](#).

The safety committee might meet to evaluate data at any time point during the conduct of the trial if deemed necessary.

12.5.2 Rules for putting the enrolment on hold

There are two pre-planned safety interim analysis. At each interim all patients exposed at the pre-defined time points determined by number of patients exposed will be evaluated for inhibitor development.

- Safety interim 1: After the first 25 patients have been to Visit 4 (20-25 exposure days)
- Safety interim 2: After the first 50 patients have been to Visit 5 (50-55 exposure days)

The expected rate of inhibitors is 30–35% in previously untreated patients with severe haemophilia A.

The rules for putting the enrolment on hold are as follows;

Inhibitor formation in 12 or more of all exposed patients at safety interim 1, or 22 or more of all exposed patients at safety interim 2, will result in the N8 safety committee evaluation of all cases of inhibitor formation. During these evaluations, ongoing treatment in the trial will continue, however new patients will not be enroled in the trial. The evaluation will provide the basis for a decision on any actions required for the trial to allow for continuation of enrolment or decision to terminate the trial.

The diagnosis of inhibitor is made if the patient has been tested positive for inhibitors (BU ≥ 0.6 mL) at two consecutive tests at central laboratory, sampled preferably within 2 weeks.

During the evaluation the safety committee will evaluate risk factors for inhibitor formation such as ethnicity, family history of inhibitors, FVIII gene mutation type, age at first FVIII treatment, reason for first treatment, treatment duration after first treatment, the details of any surgery (including type of surgery, amount of product used, and outcome), any recent infection and any recent vaccination. Furthermore the time of occurrence of inhibitor formation (after how many exposures) and whether the inhibitor is a high or low titre will be evaluated

12.5.3 Data Monitoring Committee

No Data Monitoring Committee will be established for this trial as the trial is open-label, and the investigational drug is not expected to show toxicity.

Safety surveillance will be performed by the internal Novo Nordisk safety committee.

13 Case Report Forms

Novo Nordisk will provide a system for EDC. This system and support services to the system will be supplied by a vendor. The activities of this vendor will be under the direction and supervision of Novo Nordisk.

13.1 Rules for Completing eCRFs

Ensure that all relevant questions are answered, and that no empty data blocks exist.

If a test/assessment has not been done and will not be available, or if the question is irrelevant (e.g. is not applicable) indicate this according to the data entry instructions.

The Investigator must ensure that all information derived from source documentation is consistent with the source information. By signing the case book electronically, the Investigator confirms that the information is complete and correct.

13.2 Corrections to eCRFs

Corrections to the eCRF data will be made by the Investigator or the Investigator's authorised staff. An audit trail will be maintained in the EDC application containing as a minimum: identification of the person entering the data, date and time of the entry and reason for the correction.

If corrections are made by the Investigator's authorised staff after the date of the Investigator's signature on the case book then the case book must be signed again by the Investigator.

13.3 eCRF Flow

The Investigator must ensure that data are recorded in the eCRFs as soon as possible after the visit (preferably within 3 days). When data are entered it will be available to Novo Nordisk for data verification activities.

Site specific CRF data (in an electronic readable format) will be provided to the Investigator site after the trial database is released and access to update the trial data on the EDC application is removed. These data will be retained by the site.

When the final clinical trial report (CTR) is available the data will be archived by Novo Nordisk.

13.4 Analysis Results

Laboratory reports from the Local Laboratory must be signed and dated by the Investigator on the day of the review of the analysis results. The results from the Local Laboratory should be entered in

the eCRF for each patient. A signed and dated copy of Local Laboratory report must be retained at the trial site.

Central laboratory results will be transferred electronically to Novo Nordisk.

Laboratory reports from the central laboratory will be provided to the Investigator.

14 Monitoring Procedures

During the course of the trial, the Monitor will visit the trial site to ensure that the protocol has been adhered to, that all issues have been recorded, to perform source data verification and to monitor drug accountability. The visit intervals will depend on the outcome of the remote monitoring of the eCRFs, the trial site's recruitment rate and the compliance of the trial site to the protocol and GCP. The intervals between visits must not exceed 8 weeks when there are patients ongoing in the trial at the site. When there are no trial active patients at the sites, intervals between visits must not exceed 12 weeks.

The Monitor must be given direct access to source documents (original documents, data and records). Direct access includes permission to examine, analyse, verify and reproduce any record(s) and report(s) that are important to the evaluation of the trial. In addition the Monitor should be available for discussions e.g. by telephone.

For Screening Failures: Data in respect to the Screening Visit will be entered in the eCRF within preferably 3 days after data are available. The Screening Failure Form will be completed. These data will go into the trial database.

For withdrawn patients: All data collected in the period the patient participated in the trial will be entered in the eCRF.

The following data can be recorded directly in the eCRF and will then be considered source data:

- Ethnic origin
- Race

For all other data in the eCRF, it must be possible to verify these against source documents.

Diaries on paper will be provided by Novo Nordisk. Information on treatment and bleeds will be collected in the diaries, please refer to Section [8.4.5](#). The completed diaries are considered source data. The original diary must be stored at site. The Monitor will verify and ensure that the eCRFs and diaries are completed.

For all data recorded the source document must be defined in a source document agreement at each site.

15 Data Management

Data management is the responsibility of Novo Nordisk Headquarters. Data management may be delegated under an agreement of transfer of responsibilities to another data management unit within Novo Nordisk or external clinical research organisation (CRO).

Appropriate measures such as encryption of data files will be used to assure confidentiality of patient data when it is transmitted over open networks.

Laboratory data will be transferred electronically from the central laboratory performing clinical analyses. In cases where laboratory data are transferred via non-secure electronic networks, data will be encrypted during transfer. The electronic laboratory data will be source data.

The central and local laboratories will provide laboratory reports to the Investigator. The laboratory report must be signed and dated by the Investigator and stored at the trial site as source data.

Data will be entered and delivered in an Oracle Clinical (OC) file and loading into OC.

The patient and biological material obtained from the patient will be identified by patient number, trial site and trial identification number. Appropriate measures such as encryption or deletion will be enforced to protect the identity of human patients in all presentations and publications as required by local/regional/national requirements.

16 Computerised Systems

Novo Nordisk will capture and process clinical data using computerised systems which are described in NN Standard Operating Procedures and IT architecture documentation. The use and control of these systems are documented.

Investigators working on the trial may use their own electronic systems to capture source data. Novo Nordisk will collect information on the practical use of these systems within the conduct of this clinical trial.

17 Evaluability of Patients for Analysis

All main descriptions and analyses of efficacy will be based on the Full Analysis Set, as defined in ICH E9 Guidelines (Statistical Principles for Clinical Trials)¹⁸. The Full Analysis Set includes all dosed patients with data after dosing.

The Safety Analysis Set also includes all dosed patients with data after dosing. The analyses of the safety endpoints will be based on the Safety Analysis Set.

No formal Per-Protocol analysis is planned. However, the sensibility of the results with respect to single patient's data may be investigated by performing additional analyses on subsets of data.

18 Statistical Considerations

Novo Nordisk will be responsible for the statistical analysis.

18.1 Sample Size Calculation

No formal sample size calculations have been performed. The sample size is based on the EMA guideline requirement.

18.2 Statistical Methods

18.2.1 General Considerations

No formal testing of statistical hypotheses will be performed. Evaluation of data will be based on estimated incidence rates and odds ratios, and confidence intervals for these, as well as descriptive statistics, i.e. summary tables, listings, and figures.

18.2.2 Primary Endpoint(s)

Incidence rate of inhibitors defined as inhibitor titres ≥ 0.6 Bethesda units/mL

The incidence rate of inhibitors will be calculated and a 1-sided 97.5% upper confidence limit will be provided based on an exact calculation for a binomial distribution. For the calculation of the incidence rate the numerator will include all patients with inhibitors while the denominator will include all patients with minimum of 50 ED plus any patients with less than 50 ED but with inhibitors.

Furthermore, the time to inhibitor development will be presented by a Kaplan Meyer plot. The relationship between the incidence rate of inhibitors and different patient and treatment characteristics will be investigated

Patient characteristics include:

- Ethnicity (White, Asian, African, Other)
- Family history of inhibitors (Negative, Positive)
- FVIII gene mutation type (Low risk (small deletions/insertions of < 200 base pairs, missense mutations, and other including splice or promoter mutations), High risk (large deletions of over 200 base pairs, nonsense mutations, intron 22 or one inversions))

Treatment characteristics include:

- Age at first treatment (Older than 12 months, between 6-12 months, between 1-6 months, before 1 month)
- Reason for first FVIII treatment (Prevention, Bleed, Surgery)
- Treatment moment at first treatment (Less than five consecutive days, Five or more consecutive days)

The odds ratio for each patient and treatment characteristic will be calculated using a univariate

logistics regression model and presented together with a 95% confidence interval. The incidence rate of inhibitors will be calculated and presented by the patient and treatment characteristics.

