Furthermore, physical examination, vital signs, laboratory tests, and recording of AEs and SAEs will be performed for safety assessments.

Patients with development of inhibitors

In case of inhibitor development, the clinical evaluation will take into account the inhibitor titre, and different patient and treatment characteristics.

Patients with inhibitor formation will be offered continued treatment with NNC 0155-0000-0004.

Surgery

Patients undergoing surgical procedures will receive NNC 0155-0000-0004 bleeding preventive treatment before, during and after surgery according to standard of practice of the participating site.

Trial Product

Each patient will receive bleeding preventive treatment with a dose of NNC 0155-0000-0004 (hereafter named N8) of 15-60 IU/kg BW. The exact dose of N8 is decided by the Investigator based on the patient's clinical profile. It is recommended to have at least one day between each N8 preventive dose.

The initial infusions will be administered at the investigational site, but after adequate instruction and practice the goal is to implement home treatment with intravenous (i.v.) injections given by the parent or a support person. N8 will be supplied as freeze dried powder to be reconstituted with a sterile sodium chloride solution for injection.

The dose for treatment of bleeds is decided by the Investigator but should be approximately 25-50 IU/kg in accordance with Guidelines for the Management of Haemophilia². The maximum total daily dose of N8 for the treatment of bleeds is 200 IU/kg with a maximum dose per infusion of 100 IU/kg. This maximum limit does not apply during inhibitor treatment for patients with inhibitors.

2 Flow Chart

Table 2–1 Visit Flow Chart

Visit number	Screen. Visit 1	Visit 2	Visit 3	Visit 4	Visit 5	Visit 6	Visit 7	Unscheduled Visit
PRO questionnaire	•		•				•	
HE assessment		•	•	•	•	•	•	•
Viral antibody test (if HIV, HBsAg and/or HCV status unknown)	•b							
T cells subset: CD4+	•h							
TRIAL MATERIAL								
N8 administration		•b	•	•	•	•		•b
Home treatment training		•						
Diary and Trial card dispensing and/or collection	•e	•e	•e	•e	•e	•e	•	•b
Review of patient diary and entry of data in eCRF			•	•	•	•	•	•b
Enrolment session in IV/WRS	•							
Completion session in IV/WRS							•	
Drug dispensing and accountability		•g	•	•	•	•	•g	•b
End of trial form							•	

a – minimum 48 hours washout period of N8 (or blood component products at Visit 1)

b – if applicable

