5.3.1 Preventive Treatment and Dose Adjustment

The preventive treatment regimens are meant to reflect the different dosing regimens applied globally for initial and continued treatment of PUP. The recommended dose is 15-50 IU/kg BW once weekly at the start of preventive treatment, but ~~higher and~~ more frequent doses may be necessary depending on the clinical situation. The regimen should then be gradually increased towards 20-50 IU/kg BW every second day or 20-60 IU/kg BW *two or three times weekly*.¹⁴

The decision to initiate preventive treatment will be made by the Investigator and the child's parent or legal representative with due consideration for the child's own wishes (if they are capable to express these wishes). However, the preventive treatment has to be commenced no later than when the patient reaches 24 months old, or after a maximum of two ~~treatment requiring bleeding episodes have occurred which require treatment with turoctocog alfa (joint, muscle or severe bleeding episode) have occurred~~, whatever comes first. Should a patient be older than 24 months of age at enrolment, preventive treatment needs to start immediately

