8.4.6.2 Details of haemophilia

Following information about the patient's haemophilia to be obtained during the Screening Visit (Visit 1):

- Diagnosis of haemophilia A (date)
- Classification of haemophilia A and FVIII level (%)
- Underlying gene defect (if known *and patients/LAR's consent has been obtained*)
- History of relatives with haemophilia A (as recalled by parent/guardian) including inhibitors

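### Section 18.2.2: the univariate treatment-moment odds ratio can pick up the reason for first treatment, because on the listed regimens prevention starters fall only in the under-five-days class

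*Combined protocol and SAP*

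**What the plan says.** Section 18.2.2 (Primary Endpoint) lists patient and treatment characteristics to be related to inhibitor incidence. Two of the treatment characteristics are "Reason for first FVIII treatment (Prevention, Bleed, Surgery") and "Treatment moment at first treatment (Less than five consecutive days, Five or more consecutive days"). On the model it says: "The odds ratio for each patient and treatment characteristic will be calculated using a univariate" logistic regression, with a 95% confidence interval. Incidence is also shown by each characteristic. No stratified, restricted or multivariable analysis is planned, and the term treatment moment is not defined. The later amendments to 18.2.2 leave this list and model in place. Section 18.2.4 extends the investigation to clinically relevant and high-titre inhibitors and, as amended, to the extension and combined phases.

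On preventive dosing, the Summary (Trial Product) states: "It is recommended to have at least one day between each N8 preventive dose". Section 5.3.1, as amended, states: "The recommended dose is 15-50 IU/kg BW once weekly at the start of preventive treatment". It allows more frequent doses where the clinical situation calls for them, and then moves towards dosing every second day or "two or three times weekly". Section 5.3 gives one bolus per administration day for prevention. Section 5.3.1 also allows prevention to be deferred within limits, so boys may enter treatment either by prevention or by a bleed.

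On family history, 18.2.2 has two levels, "Family history of inhibitors (Negative, Positive"). Section 8.4.6.2 collects at Visit 1: "History of relatives with haemophilia A (as recalled by parent/guardian) including inhibitors".

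**The concern.** Two characteristics that are analysed one at a time are tied together by the dosing schedule. A first treatment of five or more consecutive days is, on the listed regimens, a bleed or surgical course. A first treatment of under five days may be the start of prevention or a short bleed or surgical course. The single-factor odds ratio for duration therefore compares groups that also differ in reason for first treatment.

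At stake is the reading of a named output. Section 18.2.1 bases the evaluation on estimated incidence rates and odds ratios with confidence intervals. A report could attribute to the length of first treatment what belongs to the reason for it, or could miss a duration effect because the reason offsets it. The safety committee's evaluation under 12.5.2 also looks at both the reason for first treatment and its duration.

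**Working it through.** The plan gives no figure for this contrast, and 18.1 reports no formal sample size calculation, so there is nothing to reproduce. The check asks what the crude odds ratio would be if duration had no effect.

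**From the documents:** 50 evaluable boys (amended 18.1 and 5.3); expected inhibitor rate 30–35% (12.5.2), that is 0.30 × 50 = 15 to 0.35 × 50 = 17.5 events.

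**Assumed, because the documents do not say:** 20–60% of boys start on prevention; 30% of bleed/surgery starters have five or more days; no prevention starter does. Bleed/surgery starters have 1, 2 or 3 times the inhibitor odds of prevention starters.

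**Formula.** Let p₀ be the risk in prevention starters and p₁ the risk in bleed/surgery starters. The risk in the five-or-more class is p₁. The risk in the under-five class is r = (n_prev·p₀ + n_short·p₁)/(n_prev + n_short). The crude OR is [p₁/(1−p₁)] / [r/(1−r)].

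**Simple case.** There are 25 prevention starters at 20% and 25 bleed/surgery starters at 40%, of whom 8 (30% of 25 = 7.5, rounded) have five or more days and 17 do not.
- r = (25×0.20 + 17×0.40)/42 = 11.8/42 = 0.281
- OR = (0.40/0.60)/(0.281/0.719) = 1.71, where the true value is 1.0

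**Lower end of the range** (overall risk 35%, 10 prevention starters, odds 2 times). Here p₀ = 0.234 and p₁ = 0.379, since 0.2×0.234 + 0.8×0.379 = 0.35. There are 12 boys with five or more days and 28 short courses.
- r = (10×0.234 + 28×0.379)/38 = 0.341
- OR = 0.610/0.517 = 1.18

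**Upper end** (overall risk 35%, 30 prevention starters, odds 3 times). Here p₀ = 0.25 and p₁ = 0.50. There are 6 boys with five or more days and 14 short courses.
- r = (30×0.25 + 14×0.50)/44 = 0.330
- OR = 1.00/0.491 = 2.03

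| Odds, bleed/surgery vs prevention | Crude OR, true OR 1.0 | Crude OR, true OR 2.0 |
|---|---|---|
| 1 (equal risk) | 1.00 | 2.00 |
| 2 times | 1.18–1.58 | 2.34–3.15 |
| 3 times | 1.27–2.03 | 2.52–4.05 |

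**Reversed risks** (prevention 40%, bleed/surgery 30%; 25 in each group).
- r = (25×0.40 + 17×0.30)/42 = 0.360
- OR = 0.429/0.561 = 0.76; with 15 to 35 prevention starters it is 0.71–0.84

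**Precision.** The five-or-more class holds 6–12 boys. The 95% interval runs from the estimate divided by, to the estimate multiplied by, about 3.8–6.4. In the simple case the expected cells are 3.2, 4.8, 11.8 and 30.2. The standard error of log OR is √(1/3.2 + 1/4.8 + 1/11.8 + 1/30.2) = 0.80, so the interval is about 0.36–8.2.

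**After restriction to bleed/surgery starters** (20–40 boys), the odds ratio returns to the true value when bleed and surgery starters share one risk, as assumed here. The interval factor becomes about 3.9–8.1.

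**The case against.** Four points can be made for the plan.

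1. *The exclusion is not absolute.* The gap between preventive doses is a recommendation, 5.3.1 allows more frequent doses, and treatment moment is undefined. This stands. A reader might infer that the two factors are confounded by construction, but the documents support only a cell that is empty when a listed regimen is followed.

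2. *Overlap is not bias.* Distortion also needs a risk difference by reason for first treatment. The documents give none, and 18.2.2 lists reason as something to investigate. This stands too: with equal risks the crude odds ratio is right. But the plan cannot assume equality for a factor that it sets out to study.

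3. *The analysis is descriptive and imprecise.* Section 18.2.1 rules out formal testing, incidence is also shown by reason alone, and the interval is wider than the shift. This limits the importance of the point. It does not make the contrast interpretable, because a wide interval does not show that its centre is displaced.

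4. *Restriction still pools bleed with surgery.* This is true, and is why the incidence table should keep the three reasons apart.

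A reader might also infer that the family-history odds ratio is confounded or diluted, because boys with no affected relative would join the Negative group. The documents do not support this. No other listed factor is involved, and comparing Positive with everyone else is a legitimate choice of reference group. The coding of such boys is inferred, not stated. The direction is open as well. Assume that 30–50% have no affected relative, 20–30% of the rest are Positive, and the true odds ratio against affected-relative Negatives is 2.0. The pooled value is then 2.48–2.94 if boys with no affected relative have half those Negatives' odds, 2.00 if equal, and 1.56–1.73 if 1.5 times.

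**Conclusion.** The point holds for treatment moment, as a limit on interpretation. On any listed preventive regimen, the planned univariate odds ratio sets a bleed/surgery-only class against a mixed class and cannot separate duration from reason. With no duration effect, the expected odds ratio is about 1.2–2.0 if bleed/surgery starters have two to three times the odds, 0.71–0.84 under the reversed risks shown, and 1.0 if risks are equal. These sizes rest on the assumed shares and risks, and on regimens being followed. The primary incidence rate and its exact upper confidence limit are unaffected. Family history needs only a coding clarification. Overall this is a cheap improvement, not a flaw in the primary analysis.

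**What to change.** In 18.2.2, and for the matching high-titre and clinically relevant inhibitor analyses in 18.2.4:

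- Define treatment moment: when the first treatment starts and ends, and how consecutive days are counted when the recorded reason changes, for example when a bleed occurs soon after prevention starts.
- Calculate its odds ratio among boys first treated for a bleed or surgery, alongside or in place of the crude one.
- Present incidence cross-classified by reason (prevention, bleed, surgery) and duration (under five, five or more days).
- State how boys with no affected relative are classified for family history, and show them as a separate incidence row.

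The cost is analysis-plan wording and one extra table, from data already collected. The restricted odds ratio uses perhaps 20–40 of 50 boys and has a wider interval. With 6–12 boys in the longer class it stays descriptive, and 15–18 events would not support a large multivariable model instead.
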